#### **9.1.2.5 Physical Function**

Improvement in physical function is assessed by the change from baseline (original study) in HAQ-DI at week 48, 96, 144, 192, 240, 264, and EOT, if EOT is prior to Week 264. It is based on the HAQ-DI assessment that is completed at each visit by the patient, as one of the ACR components.

The HAQ-DI is composed of 8 categories as follows: dressing and grooming, arising, eating, walking, hygiene, reach, grip and activities, for which there are at least 2 questions by category. The patient will be asked to score how difficult he/she feels it is to perform such activities using a 0 to 3 scoring (0=without any difficulty, 1=with some difficulty, 2=with much difficulty and 3=unable to do). If the patient is using assistance for any of these activities, scoring may be adjusted. For each category, the highest score given for one of the question is attributed to the category. The total score is the sum of all categories' scores divided by the number of answered categories (at least 3 categories should be answered) (see [Appendix J](#)).

#### **9.1.2.6 ACR Components**

Each component of the ACR will be analysed as other secondary outcomes over time.

All ACR components will be assessed up to Week 264.

After Week 264, TJC and SJC (both based on 28 joints), patient's global assessment of disease activity and hs-CRP will still be assessed to calculate DAS28.

#### **9.1.2.7 Health economic assessment and Patient reported outcomes (PROs)**

- Health economic assessments and PROs will be performed up to Week 264 as defined in the initial study and as specified in the study flowchart (See section 1.2).

- The Functional Assessment of Chronic Illness Therapy Fatigue scale (FACIT-Fatigue) will be used to assess fatigue. The FACIT-Fatigue is a 13-item questionnaire rated 0 to 4 originally developed to measure fatigue in patients with cancer and widely used in rheumatoid arthritis patients that demonstrates good consistency and sensitivity to change. The patient will be asked to answer 13 questions rated 0 to 4 (0 = not at all, 1 = a little bit, 2 = some what, 3 = quite a bit, 4 = very much) (see [Appendix F](#)). The patient will be asked to fill in the questionnaire at different site visits (see flow chart, [Section 1.2](#))
- The Work Productivity and Activities Impairment (WPAI) will be assessed for patients coming from EFC11072 and ACT11575 only. The WPAI was developed by Margaret Reilly for assessing productivity losses by measuring the effect of general health and symptom severity on work as well as usual activity productivity. Specific-disease WPAI exists and can be adapted to different pathologies. The RA WPAI ([Appendix G](#)): instrument consists of 6 questions that ask the subject the number of hours missed from work (ie, absenteeism) due to RA, the number of hours missed from work for anything other than RA, the number of hours totally worked, as well as how much the RA does affect the productivity at work or the ability to do daily activities over the past 7 days. The instrument can be self-, interview-, or telephone-administered and takes less than 5 minutes to complete (~3 minutes). The 4 scores of the questionnaire are expressed as impairment percentages with higher numbers reflecting greater impairment and decreased productivity. The 4 scores are:
  1. Percent work time missed due to RA
  2. Percent impairment while working due to RA
  3. Percent overall work impairment due to RA
  4. Percent activity impairment due to RA
- The WPAI has been tested in many disease states including migraine, arthritis, hypertension, diabetes, and depression and is adaptable to specific health problems such as RA. Inclusion of this measure in the study assesses the impact of sarilumab on a major component of subjects' lives, which is their ability to perform daily activities and/or be able to work. The patient will be asked to fill in the questionnaire at different site visits (see flow chart, [Section 1.2](#))
- Assessment of joint replacement and joint procedures if any will be performed: total joint replacement (arthroplasty).
- Sleep: Rheumatoid arthritis, like other chronic illness, is associated with sleep disturbances. Sleep disturbance is linked to pain, mood, and disease activity. The effect of sarilumab on pain will be assessed on a VAS scale (see [Appendix H](#)). The patient will be asked to fill in the questionnaire at different site visits (see flow chart, [Section 1.2](#))
- SF-36: The Short-Form 36 (SF-36) is a generic questionnaire measuring general health status (quality of life). It is one of the most frequently used and has been extensively validated in rheumatologic disease (see [Appendix I](#)). The patient will be asked to fill in the questionnaire at different site visits (see flow chart, [Section 1.2](#))

- The Rheumatoid Arthritis-Work Productivity Survey (WPS-RA): The WPS-RA is a validated questionnaire that evaluates productivity limitations within work and within home associated with RA over the previous month.

It is interviewer-administered, is based on patient self-report. It contains 8 items that include 3 work productivity related items and 5 home productivities related items (household activities) (see [Section 27](#), [Appendix Q](#)) plus 1 item related to the employment status.

#### Within work

- Number of days of work missed
- Number of days with productivity  $\leq 50\%$  at work
- Arthritis interference with work productivity on a scale of 0 to 10 (0 = 'no interference' and 10 = 'complete interference')

#### Within the home

- Number of days of household work missed
- Number of days with productivity  $\leq 50\%$  in household work
- Number of days of family, social, or leisure activities missed
- Number of days with outside help
- Arthritis interference with household work productivity on a scale of 0 to 10 (0 = 'no interference' and 10 = 'complete interference')

## 9.2 DELETED

## 9.3 PHARMACOKINETICS AND IMMUNOGENICITY

Pharmacokinetics and immunogenicity assessment will be performed in all patients.

### 9.3.1 Sampling time

Serum samples will be collected for determination of functional sarilumab, anti-sarilumab antibody (also known as anti-drug antibody (ADA)) and IL-6 according to the Study Flow Chart ([Section 1.2](#)). The date of collection should be recorded in the e-CRF.

Serum concentrations of bound (serum sarilumab-sIL-6R $\alpha$  complex) and functional sarilumab were intended to be analyzed in the study. After the completion of EFC11072 Part B study, the Sponsor made the decision to only analyze functional sarilumab concentrations.

If a serious adverse event (SAE) occurs in a patient, serum samples should be collected for determination of sarilumab at or near the onset and completion of the occurrence of the event, if possible. The exact date of sample collection and last dose must be recorded on the e-CRF.

### 9.3.2 Pharmacokinetic handling procedure

Special procedures for collection, storage and shipping of serum will be described in separate operational manuals.

An overview of sample handling procedures for pharmacokinetics (PK), anti-sarilumab antibody, and IL-6 is provided below:

**Table 1 - Summary of handling procedures for sarilumab, anti-sarilumab antibody, and IL-6**

	Sarilumab	Anti-sarilumab antibody	IL-6
Blood Sample Volume	6 mL	6 mL	2.5 mL
Anticoagulant	None	None	None
Blood Handling Procedures	See Operational Manual	See Operational Manual	See Operational Manual
Serum Aliquot Split	Two aliquots	Two aliquots	One aliquot
Serum Storage Conditions	< 6 month: below -70°C (preferred) / -20°C > 6 month: below -70°C	< 6 month: below -70°C (preferred) / -20°C > 6 month: below -70°C	-20°C
Serum Shipment Condition	In dry ice	In dry ice	In dry ice

### 9.3.3 Bioanalytical method

Serum samples will be assayed using validated methods as described below:

**Table 2 - Summary of bioanalytical methods for sarilumab and anti-sarilumab antibody**

Bioanalysis	Sarilumab	Anti-sarilumab antibody
Matrix	Serum	Serum
Analytical Technique	ELISA	Electrochemiluminescence
Site of Bioanalysis	Regeneron	Regeneron

In addition, IL-6 will be measured using validated assays.

## 9.4 SERUM AND RNA BIOMARKERS

Please refer to the LTS11210 operations laboratory manual for a description of the collection, handling, storage, and shipment of the biomarker specimens.

Potential studies may include examining markers related to IL-6 signaling, response to sarilumab, or related to the disease of RA. It is anticipated that the serum and RNA biomarker samples will be stored for up to 15 years (or as appropriate, according to applicable regulations) after completion of the final report of the main clinical trial. Storage after the end of the study will be at an accredited, dedicated long term biological sample storage facility which has established a strict and comprehensive security and confidentiality system. Samples will remain the property of the Sponsor and will be used only for the purposes described here, upon request by the Sponsor.

### 9.4.1 Serum for future biomarker analysis

A serum sample (5 ml) will be collected for future biomarker analysis at the EOT visit of the initial study, and at Week 2, Week 12, and Week 48 (except EFC13752 patients).

### 9.4.2 RNA for future biomarker analysis

Whole blood samples for ribonucleic acid (RNA) expression profiling (non-genetic analysis) will be collected at Week 0 (V2 or V1/V2), prior to treatment, and at Week 2/Visit 3 site visits only (except for SFY13370 and EFC13752 patients).

If week 2/Visit 3 is scheduled as a “home visit”, the whole blood sample for RNA will not be collected.

## 10 PATIENT SAFETY

### 10.1 SAFETY PARAMETERS ASSESSED IN THIS TRIAL

- **Adverse events:** at every visit, the Investigator will ask the patient how he has felt since the last study visit.
- **Vital signs:**
  - Vital signs including temperature, blood pressure, and heart rate will be collected prior to dosing per specifications on the study flow chart (see [Section 1.2](#)):
  - Body temperature will be collected using the same method for a given patient. Any fever: body temperature  $\geq 38^{\circ}\text{C}$  should be recorded as an adverse event and the Investigator should perform all investigations necessary to rule out infection (see [Section 10.2](#)).
  - Blood pressure will be measured under standardized conditions, using the same well calibrated apparatus. Both systolic and diastolic blood pressure should be recorded. Supine or sitting blood pressure should be checked after 2 minutes of rest. Standing blood pressure is obtained 1 minute after the patient stands up. The same arm should be used to measure blood pressure throughout the study.
- **Physical examination:** A complete physical examination including a neurological examination will be performed as specified in the flowchart (see [Section 1.2](#)). Any clinically significant abnormalities should be reported in the patient e-CRF as an adverse event. Body Weight should be taken on a regular basis per specifications on the study flow chart (see [Section 1.2](#)) Body weight should be obtained with the patient wearing undergarments or very light clothing and no shoes, and with an empty bladder. The same scale should be used throughout the study.
- **Tuberculosis assessment:** (see [Section 1.2](#) and [Section 10.2](#))
- **Electrocardiogram (ECG):** A standard 12-lead ECG will be performed as specified in the flowchart (see [Section 1.2](#)). Heart rate, QRS duration, PR interval, QT interval, ST deviation, T-wave morphology, U wave presence or absence will be determined using a centralized automatic and manual reading of all ECG.
- **Laboratory safety:** Blood will be taken before study drug dosing at the study site or at home by qualified personal. The following laboratory tests will be performed per specifications on the study flow chart (see [Section 1.2](#)):
  - Hematology  
Including: Hemoglobin, hematocrit, Red Blood Cell (RBC) morphology (if blood cell count is abnormal), WBC with differential, and platelet count

- Liver Function Test  
Including: Prothrombin Time (PT), albumin, Alanine Aminotransferase (ALT), Aspartate Aminotransferase (AST), Alkaline Phosphatase (ALP), total bilirubin, conjugated bilirubin, unconjugated bilirubin. NOTE: after Week 264, PT will no longer be tested.
- Lipids profile (patients need to be fasting)  
Including: total cholesterol (TC), High Density Lipoprotein (HDL) cholesterol, Low Density Lipoprotein (LDL) cholesterol, triglycerides, Apolipoprotein A and Apolipoprotein B (Apolipoprotein A and B determination is not performed in SFY13370 study and results will not be available for the initial LTS11210 visit for SFY13370 patients). NOTE: after Week 264, only total cholesterol, HDL cholesterol, LDL cholesterol and triglycerides will be tested.
- Clinical Chemistry (patients need to be fasting)  
Including: fasting glucose, total protein, calcium, sodium, potassium, Lactate Dehydrogenase (LDH), urea nitrogen and creatinine. Creatinine clearance will be calculated only at initial visit and during the study if clinical indicated.
- For women of child-bearing potential: urine pregnancy testing will be performed as per study flow chart in [Section 1.2](#). From V6, the site will dispense urine pregnancy kits to the patients who will perform the test at home on a monthly basis. The pregnancy test should be completed prior to any X-ray procedure. If any interim urine pregnancy test performed by the patient is positive, the patient should immediately report to the investigator for appropriate follow-up and pregnancy reporting as appropriate.
- Urine analysis: including specific gravity, pH, glucose, blood, ketones, proteins, bilirubin, urobilinogen, nitrate, leukocytes will be performed per specifications on the study flow chart using a dipstick. If any parameter is abnormal, a urine sample should be sent to the central laboratory for testing. If positive for proteins, microscopic analysis will also be performed by central laboratory. NOTE: after Week 264, urine analysis will no longer be performed.
- ANA/Anti-ds-DNA: testing will be done per specifications on the study flow chart (see [Section 1.2](#)).
- Hepatitis B and C: serology will be determined as clinically indicated (see [Section 10.2.4](#)).
- HIV: testing will be done anytime during the study when the patient has been at risk for HIV infection as per investigator judgment.  
  
Note: Local regulations or recommendations regarding regular eg, yearly HIV testing should be followed using a central or local laboratory facility.
- Anti-sarilumab antibody: testing will performed per specifications on the study flow chart (see [Section 1.2](#))

**Note that the laboratory values from the end of treatment in the study EFC11072, ACT11575, EFC10832, SFY13370, or EFC13752 studies will be the laboratory values for the initial visit of the LTS11210 study.**

Specimens will be submitted for analysis as per the instructions of the central laboratory.

## 10.2 SAFETY INSTRUCTIONS

### 10.2.1 Infections

Biologics including TNF- $\alpha$  inhibitors and tocilizumab (another IL-6 receptor inhibitor similar to sarilumab) have been associated with an increased risk of infection, including black box warnings for serious infections leading to hospitalization or death.

In the ongoing phase 3 program, serious infections including life threatening sepsis, have been reported, some notably associated with minor trauma. As a precautionary measure, investigators should carefully follow any signs of infection with particular care to identify potential infective complications in immune-suppressed individuals where superficial skin wounds or abrasions may lead to serious infections including necrotizing fasciitis and/or sepsis.

Any infection should be reported by the Investigator as an adverse event and a corresponding e-CRF form should be filled in. Treatment with antibiotics if any should be recorded with the route of administration.

- **Clinically significant infection:** [Section 10.5.4](#) defines clinically significant infections that require pre-specified monitoring and should be reported as adverse events of pre-specified monitoring/adverse events of special interest (AEPM/AESIs) with immediate notification. In case of suspicion of clinically significant infection, a complete diagnostic work-up should be performed including but not limited to cultures for bacterial infections, fungi and/or mycobacteria, histopathological or cytological evaluation, antigen detection and serum antibody titers. The type of infection should be listed in the e-CRF form. The patient should be referred to a specialist if needed for diagnosis and treatment. In addition, the study Investigator should determine if the infection qualifies for serious adverse event reporting or not.
- Note: Systemic opportunistic infections should be reported as serious.
  - The IMP should be temporarily discontinued in case of infection requiring oral or parenteral treatment with antibacterial, antiviral and/or antifungal agents (See [Section 11.1](#)) or permanently discontinued in case of confirmed opportunistic infections including but not limited to TB. (See [Section 11.2.1](#) and [Appendix M](#)).
- **Tuberculosis assessment:** Sarilumab is a biologic treatment that may induce immunosuppression, including the risk of reactivation of latent tuberculosis. A special warning of the increased risk of tuberculosis is included in the labels of TNF antagonists and tocilizumab.

As a precautionary measure, patients at risk for tuberculosis will be permanently discontinued from the study.

A clinical examination and history will be performed at every visit to assess any signs and symptoms of tuberculosis or contact with a patient with active tuberculosis.

A QuantiFERON TB Gold test can be performed at any time during the course of the study in case of suspicion of tuberculosis. A chest X-ray should be performed in all patients with suspected tuberculosis.

In case of suspicion of TB, the Investigator should refer the patient to a specialist for a complete examination. The study drug should be discontinued until TB is ruled out.

Repeat chest radiographs should be performed as indicated by local treatment guidelines or practice for monitoring while on immunosuppressive/immunomodulatory therapy. If such guidelines are not available/ applicable, a chest X-rays should be performed when clinically indicated.

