
ASSESSMENT SCHEDULE
	
The last visit (EOT visit) of EFC11072, ACT11575, EFC10832, SFY13370, or EFC13752 will be used as the initial LTS11210 visit. All patients who agree to participate in the LTS11210 will need to sign a new informed consent form specific for this study. At D1, after confirmation of eligibility, patients will be enrolled in the LTS11210 study.
 
Patients will have site visits at weeks 4, 8, and 12, then every 12 weeks until the 2nd year of treatment in the study (Week 96). After 2 years of study participation, safety assessment and laboratory tests will take place at 24-week intervals. In addition, there will be visits at 24-week intervals in between regular study visits for distribution of IMP kits and recording of AEs only (in Portugal and Sweden, hematology and liver function test evaluations will be performed at all IMP dispensing visits until end of treatment). After 264 weeks in LTS11210, some assessments will no longer be required in either scheduled visits or EOT visit (see Section 1.2).
 
Additional laboratory testing (central) including hematology and liver function tests will be performed at week 2, week 6, and week 10 (site or home visits).
 
Efficacy assessments will be performed at Weeks 0, 4, 8, 12 and then every 12 weeks up to Week 96 and then every 24 weeks until the end of treatment.
 
Health economic assessments and Patient Reported outcomes (PROs) defined per initial study will be performed every 12 weeks up to Week 96 and then every 24 weeks until Week 264. PROs will not be assessed after Week 264, including EOT if EOT is after Week 264.
 
Patients who completed EFC11072 Part B will have an additional X-ray evaluation at week 48, 96, 144, 192 (<math>\pm 14</math> days for each evaluation) or at EOT if EOT prior to Week 192.
 
Electrocardiograms (ECGs) will be performed at the initial visit, week 48, 96, 144, 192, 240 and 264 or EOT. ECGs will not be performed after Week 264, including EOT if EOT is after Week 264.
 
Adverse events will be collected throughout the study.
 
Pharmacokinetic samples will be collected at V1 or V1/V2, V4 (Week 4), V7 (Week 12), every 12 weeks thereafter through year 2 and then every 24 weeks until the end of treatment and at the Post-Treatment follow-up visit 6 weeks after the end of treatment.

[figure not shown]

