### **11.2.1 List of criteria for definitive treatment discontinuation**

The patients may withdraw from treatment with IMP if they decide to do so, at any time and irrespective of the reason, or this may be the Investigator's decision. All efforts should be made to document the reasons for treatment discontinuation and this should be documented in the e-CRF.

Study drug will be permanently discontinued in case of the following events:

- Confirmed diagnosis of opportunistic infection based on the investigator's assessment following diagnostic workups and expert consultations
- Active tuberculosis:
  - the diagnosis can be made either on symptoms or on a chest radiograph suggestive of active TB. Patients should be referred to appropriate medical specialists and whenever possible, culture confirmation of disease should be obtained and recorded in the e-CRF.
- The patient is at risk through close contact with a person with active TB and the patient refuses to undergo TB evaluation.
- Culture positive for non-tuberculosis mycobacteria
- Symptoms of systemic hypersensitivity or anaphylactic reactions.
- Severe neurologic disease such as demyelinating disease or PML.
- Significant laboratory abnormalities:
  - ALT > 5xULN or ALT > 3xULN with concomitant total bilirubin > 2xULN (unless patient with documented Gilbert's syndrome)
  - neutrophil count < 500/mm^3, or neutrophil count < 1000/mm^3 with evidence of infection

- platelet count  $<50\,000/\text{mm}^3$ , or platelet count  $<100\,000/\text{mm}^3$  with evidence of bleeding (see [Section 10.2](#)).
- Conversion to HIV positive status
- Acute renal failure
- Pregnancy in female participant.
- Use of any biologic DMARDs other than IMP, or use of any JAK inhibitor
- For EFC13752 patients: use of any non-biologic DMARDs
- Any adverse events, per investigator judgment, that may jeopardize the patient safety.

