- ECG at week 48, 96, 144, 192, 240 and 264.
- Perform a complete joint examination to assess tender and swollen joints.
- Ask the patient to complete relevant questionnaires: HAQ, patient's global assessment, patient's pain questionnaire.
- Ask the patient (except for SFY13370 and EFC13752 patients) to complete health economic assessments as per initial study (See [Section 1.2](#)).
- Complete the physician global assessment.
- Dispense Investigational Product (12-week supply) and remind instructions on self-injection and dosing; and provide self-injection diary.
- The study coordinator or designee will administer the subcutaneous injection (if  $14 \pm 3$  days from last administration) and will observe the patient for 30 minutes.
- Dispense urine pregnancy test kits for monthly urine pregnancy test.

- Schedule appointment for next visit.
- The Investigator should check the results of the LFTs, neutrophil and platelet counts as soon as received and take any necessary action to ensure patient safety, including per protocol-specified rules for dose reduction, and permanent treatment discontinuation.

**12.1.10 Visit 15 (Week 108), Visit 17 (Week 132), Visit 19 (Week 156), Visit 21 (Week 180), Visit 23 (Week 204), Visit 25 (Week 228), Visit 27 (Week 252), Visit 29 (Week 276), Visit 31 (Week 300), Visit 33 (Week 324), Visit 35 (Week 348), Visit 37 (Week 372), Visit 39 (Week 396), Visit 41 (Week 420), Visit 43 (Week 444), Visit 45 (Week 468), Visit 47 (Week 492): IMP dispensing visits in between 24-week on-treatment visits (after Week 96)**

This section refers to the IMP dispensing visits that will occur every 24 weeks from week 108 to week 492, alternating with the visits at which clinical assessments are performed.

After Week 96, at 12-week intervals in between the q 24-week on-treatment visits the Investigator will:

- Check compliance to the study drug and concomitant medication and record any changes in the patient's CRF.
- Obtain blood sample for hematology and LFTs (applicable for Portugal and Sweden only; no PT required after Week 264).
- Inquire regarding AE/SAEs.
- Dispense Investigational Product (12-week supply) and remind instructions on self-injection and dosing; and provide self-injection diary.
- Schedule appointment for next visit.

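### TB history, including contact, is required at every visit by Protocol 10.2.1 but is missing from the dispensing visits after Week 96, so contact in a well patient may be asked about 12 weeks later than that section requires

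*Protocol*

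**What the plan says.** Protocol Section 10.2.1 (Infections) sets the rule: "A clinical examination and history will be performed at every visit to assess any signs and symptoms of tuberculosis". The same sentence also covers contact with a patient who has active TB. The section adds that "As a precautionary measure, patients at risk for tuberculosis will be permanently discontinued from the study". Testing is reactive: "A QuantiFERON TB Gold test can be performed at any time during the course of the study in case of suspicion of tuberculosis". Repeat chest films follow local guidance or clinical indication.

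The schedule reads differently. The Clinical Trial Summary says "After 2 years of study participation, safety assessment and laboratory tests will take place at 24-week intervals", and that "there will be visits at 24-week intervals in between regular study visits for distribution of IMP kits and recording of AEs only". In both flow charts (Sections 1.2.1 and 1.2.2) the TB row is marked at the assessment visits, end of treatment and follow-up, and is blank in the Week 108 to 492 dispensing column. The SAP's copies in Section 1.4.3 show the same.

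Section 12.1.10 states: "This section refers to the IMP dispensing visits that will occur every 24 weeks from week 108 to week 492". Its task list covers compliance, concomitant medication, adverse-event inquiry, dispensing and the next appointment, plus blood tests in Portugal and Sweden. It has no TB item. Drug is handed over at each of these visits: "Dispense Investigational Product (12-week supply) and remind instructions on self-injection and dosing; and provide self-injection diary".

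Section 10.1 points to both Section 1.2 and Section 10.2 for the TB assessment and does not say which governs. Section 11.2.1 lists active TB as one reason to stop study drug and, separately, "The patient is at risk through close contact with a person with active TB and the patient refuses to undergo TB evaluation".

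**The concern.** A site cannot satisfy both texts as they stand. If it follows the schedule, it departs from 10.2.1 at every dispensing visit. If it follows 10.2.1, it performs a procedure that neither Section 1.2 nor 12.1.10 asks for.

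What is at stake is the contact question. Contact with an active case, in a patient who feels well, is neither an adverse event nor a medication, so nothing in 12.1.10 leads the site to ask before a further 12 weeks of drug is dispensed. Two rules depend on the site learning of contact or risk: the at-risk sentence in 10.2.1, and the contact-with-refusal criterion in 11.2.1. No other study-wide TB check is scheduled that would fill the interval.

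**Working it through.** No sample size, power or analysis figure is involved. The check is to read the TB row against the visit headers and count visits.

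**Inputs**
- Dispensing visits: every 24 weeks from Week 108 to Week 492 (12.1.10).
- Assessment visits after Week 96: every 24 weeks from Week 120 to Week 504, each with a TB item (12.1.9, 12.1.11).
- Dosing: every 2 weeks (8.1).

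**Dispensing visits without a TB item**
- Before Week 264: (252 − 108)/24 + 1 = 7.
- To Week 492: (492 − 108)/24 + 1 = 17. The visit numbers agree: V15 to V47, odd numbers only, gives (47 − 15)/2 + 1 = 17.

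**All scheduled visits after Week 96**
- To Week 264: (264 − 108)/12 + 1 = 14, so 7 of 14 lack a TB item.
- To Week 504: (504 − 108)/12 + 1 = 34, so 17 of 34 lack one.

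**Interval between TB checks after Week 96**

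| Source | Interval | Doses per interval |
|---|---|---|
| 10.2.1, every visit | 12 weeks | 12/2 = 6 |
| Section 1.2 and Section 12 | 24 weeks | 24/2 = 12 |
| Difference | 12 weeks | 6 |

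**What the difference means for one contact**
- Contact at Week 97: asked about at Week 108 under 10.2.1 and at Week 120 under the schedule, so 120 − 108 = 12 weeks later.
- Contact at Week 110: asked about at Week 120 under both, so no delay.

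The added delay is therefore 12 weeks (6 doses) when contact falls between an assessment visit and the next dispensing visit, and zero when it falls in the other half of the cycle.

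**What the dispensing visit would still pick up**
- TB symptoms: probably, through adverse-event inquiry (12.1.10).
- TB treatment: probably, through concomitant-medication review (12.1.10). TB, or starting medication for suspected TB, must also be notified within 24 hours (10.5.4).
- Contact in a well patient: not prompted.

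The Week 2, 6 and 10 blood-draw visits also lack a TB item. They are not counted here, because in the first 12 weeks they sit between visits at Weeks 4, 8 and 12 that do carry one.

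**The case against.** The strongest reply is that the working schedule is consistent and only one sentence is out of line. The summary, both flow charts and Sections 12.1.9 to 12.1.11 separate full assessment visits from light dispensing visits and place TB assessment on the former. Section 10.2.2 uses a similar every-visit instruction for signs of progressive multifocal leukoencephalopathy, and 12.1.10 has no item for that either, which suggests general wording that was not updated. The phrase also cannot be applied literally to the early blood-draw visits. On this view 24 weeks was intended, and one clause in 10.2.1 needs correcting.

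Most of this stands. A 24-week interval may well be what the sponsor meant, and the SAP charts are copies, not independent evidence. It does not remove the conflict, since 10.1 sends sites to both texts. Nor does it answer the contact question, which a rewording alone would leave at 24 weeks.

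A reader might infer more than the documents support:
- That TB goes unmonitored at these visits. Adverse-event inquiry, medication review and the 24-hour notification remain in place.
- That TB stopping rules in general are disabled. Active TB is a separate criterion in 11.2.1 and does not depend on the contact question. Under that list, contact alone does not stop drug unless the patient also refuses evaluation; only the broader at-risk sentence in 10.2.1 goes further.
- That every patient has 17 such visits. That needs follow-up to Week 492. UK patients stop at Week 264, as do patients elsewhere if sarilumab is commercially available in their country by then.
- That the safety analysis is affected. The SAP identifies TB from reported adverse events (Table 1), not from the TB row of the flow chart.

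**Conclusion.** The inconsistency is real and worth correcting, but its practical effect is small. It amounts to 7 dispensing visits for a patient who reaches Week 264 and up to 17 for one who stays to Week 492, with a TB interval of 24 weeks under the schedule against 12 weeks under 10.2.1. The residual gap is unvolunteered contact in a well patient, asked about at most 12 weeks and 6 doses later. It bears on the at-risk rule and the contact rule only.

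This assumes that visits occur as scheduled and that adverse-event inquiry and medication review work as intended. The documents give no TB incidence or contact rate, so the number of patients affected cannot be estimated. No endpoint or analysis changes.

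**What to change.** 1. Add a short TB symptom and contact history to Section 12.1.10 and to the dispensing column of both flow charts. The TB item already written for Visit 2 in Section 12.1.2.1 can be reused.
2. Reword 10.2.1 so that the clinical examination applies at the visits marked in Section 1.2 and the history also applies at dispensing visits, with the Week 2, 6 and 10 blood-draw visits excepted.

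The cost is amendment wording and a few minutes of site time at each dispensing visit (7 for a patient who reaches Week 264, up to 17 for the longest-staying). No test or visit is added.

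If the sponsor intends 24 weeks and wants no added procedure, the minimum is to limit the every-visit clause in 10.2.1 to the visits marked in Section 1.2. That takes no site time and removes the conflict, but contact is then asked about only every 24 weeks after Week 96.
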